1 OBJECTIVES

- 1.1 Primary Objective:
- 1.1.1 To evaluate the safety and tolerability of ruxolitinib in CMML subjects at diagnosis or relapse.
- 1.1.2 To determine overall response rates as measured by the international working group criteria (2006).
- 1.2 Secondary Objectives:
- 1.2.1 To determine the time to AML transformation of subjects on Ruxolitinib.
- 1.2.2 To determine the median overall survival.
- 1.2.3 To determine the duration of response achieved as in secondary endpoint one.
- 1.2.4 To determine the change in symptom score from baseline to best response.
- 1.2.5 To determine the change in spleen length at 16 weeks
- 1.2.6 To determine the change in downstream targets of JAK2 on ruxolitinib.
- 1.2.7 To determine if the *in vitro* activity of ruxolitinib correlates to response rates.
- 1.2.8 To determine if a correlation exist between the presence of the known recurrent mutations (JAK2, c-CBL, N-RAS, K-RAS, RUNX-1, TET2, SRSF2, EZH2, ASXL1, and DNMT3a) and response to ruxolitinib. .
- 1.2.9 To determine non-V617F JAK2 mutations at end of study or progression and their clinical relevance in the context of ruxolitinib.

We recognize that this is a small study and the secondary objectives are of exploratory nature.

2 BACKGROUND

2.1 Chronic Myelomonocytic Leukemia

Chronic Myelomonocytic Leukemia (CMML) is a clonal malignancy characterized by cytopenias with or without leukocytosis, marrow dysplasia, monocytosis, splenomegaly, and a propensity to transform to acute myeloid leukemia¹. Prior to 2001, the World Health Organization (WHO) classified CMML as a subtype of the myelodysplastic syndromes (MDS)². However because CMML exhibits clinical and pathologic features of a MDS and of a Myeloproliferative Neoplasm (MPN), it was reclassified by the WHO as a member of the Myelodysplastic/Myeloproliferative

Neoplasms (MDS/MPN) highlighting its nosologic complexity. CMML shares this WHO designation with atypical Chronic Myeloid Leukemia (aCML), Refractory Anemia with Ringed Sideroblasts and Thrombocytosis (RARS-T), and the pediatric counterpart of CMML, Juvenile Myelomonocytic Leukemia (JMML)³. JMML is a lethal pediatric malignancy with clinical features similar to CMML and hallmarked by selective hypersensitivity to GM-CSF⁴. The reclassification of CMML has been substantiated by next generation sequencing techniques that have allowed for the massive genetic sequencing of myeloid malignancies^{5,6}. The occurrence of recurrent mutations in CMML and MDS are now known to be different in both type and/or frequency suggesting that these diseases represent distinctly different entities. The clinical behavior of CMML is unique in that it displays features of an MDS and of an MPN within the same patient. However, CMML subjects can display the predominant features of an MDS-like or MPN-like disease. The French-American-British (FAB) group was first to subdivide CMML subjects into an MDS variant and MPN variant based on a white blood cell (WBC) count greater than 20K/dL7. The WHO later favored subdivisions based on a myeloblast percentage greater than 10% in the bone marrow aspirate because of its prognostic value³. Irrespective of these subdivisions, recent genomic advances have yet to translate to effective, CMML specific therapies and thus the current standard-of-care in CMML remains the use of drugs developed for MDS.

For instance, in 2009, Fenaux and colleges reported the results of a randomized phase III trial that demonstrated a survival advantage (24.5mo vs 15mo) for 5-azacitidine, a DNA methyltransferase (DNMT) inhibitor, when compared with induction chemotherapy, low dose cytarabine, or best supportive care in subjects with higher risk MDS and CMML. However, only 22 CMMLs were included in this study and unequal randomization did not allow for subset analysis of these subjects⁸. Despite this, 5-azacitidine gained FDA approval for the treatment of CMML and has become the first line therapy of choice. Subsequent retrospective reports have suggested that the rates of hematologic improvement in CMML are similar to MDS but that this similarity is lost when analyzing the myeloproliferative variant of CMML alone. The

myeloproliferative variant appears to be have response rates on the order of 10-15%.

Chronic Myelomonocytic Leukemia (CMML) is a rare disease with an incidence of approximately 0.3 per 100,000. The prognosis is poor with a median overall survival ranging between 12 and 20 months that is not known to be improved by 5-azacitidine¹⁰. Allogeneic stem cell transplant (ASCT) remains the only potential curative therapy. However, most subjects are ineligible secondary to age related exclusion. Those that can undergo transplant face a high degree of morbidity and unacceptable transplant related mortality with only a small fraction of subjects alive at 5 years¹¹. From an economic perspective, an ASCT is costly as are the prophylactic antibiotics necessary to prevent life threatening infection and the immunosuppressants needed to control graft versus host disease as a result of the transplant. To make matters worse, there are very few clinical trials available in CMML relative to other hematologic malignancies. This, in combination with its dismal prognosis and lack of standard therapies makes the outlook of subjects with CMML quite grim. There is a clear need for new CMML-specific therapies in this orphaned disease.

2.2 GM-CSF signaling and Chronic Myelomonocytic Leukemia

GM-CSF hypersensitivity, as defined by increased hematopoietic colony formation in methylcellulose when exposed to low dose GM-CSF, has been a known feature of JMML for over a decade⁴. The obvious clinical similarities between JMML and CMML have lead to studies, including our own, investigating the nature of GM-CSF signaling in CMML. The first such study in 2002, Ramshaw and colleges showed that spontaneous hematopoietic colony growth could be achieved in CMML patient samples and that this was inhibited by E21R, a GM-CSF specific antagonist, suggesting that autocrince or paracrine production of GM-CSF was important to *in vitro* CMML cell proliferation and differentiation. They also performed transplantation experiments in a NOD/SCID murine model that was transgenically modified to secrete human GM-CSF or not. Only those CMML cells transplanted in the GM-CSF transgenic mouse engrafted demonstrating an *in vivo* requirement for proliferation¹². In the next study, Kotecha and colleges explored the downstream

signals elicited by the GM-CSF receptor in JMML. Despite the fact that JMML is predominantly a RAS-mediated disease, Kotecha and colleges demonstrated that it was STAT5 and not ERK that was hyperphosphorylated in the presence of GM-CSF. This phenomenon was not seen in normal controls or other pediatric MPNs but was seen in five CMML patient samples¹³.

Our laboratory has confirmed these results by demonstrating that CMML primary samples are sensitive to very low doses of GM-CSF as measured by STAT5 phosphorylation (n=20)¹⁴. We have also shown that GM-CSF inhibition is important to CMML viability by introducing KB-003, a highly specific monoclonal antibody to GM-CSF developed by KaloBios pharmaceuticals. Despite the molecular and clinical heterogeneity observed in CMML, all samples tested (n=10) showed decrease proliferation and viability when exposed to GM-CSF blockade and the vast majority of samples tested (n=20) showed GM-CSF dependent STAT5 activation (Yp) at lower doses of GM-CSF compared to controls and compared to other cytokines within the CMML subjects. Further it was the immature monocytes (CD33+/CD14+) that seemed most sensitive to this inhibition, leaving the rest of the bone marrow unaffected.

2.3 Ruxolitinib

Ruxolitinib is an FDA-approved agent for the treatment of myelofibrosis. It is a potent inhibitor of JAK1 and JAK2 (nM IC50) that has been tested in a wide array of JAK/STAT dependent processes. In JAK/STAT dependent cell lines, ruxolitinib demonstrates IC50 values of 80-300 nM and can inhibited JAK/STAT signaling and growth in cell lines expressing the constitutively active JAK2 mutant (JAK2V617F) that is present in approximately 15% of CMML subjects⁵. The JAK2V617F abnormality has been broadly implicated in the pathogenesis of the majority of Philadelphia chromosome negative MPNs. It is because of this that INCYTE, the makers of ruxolitinib, have targeted MPNs in its initial drug development. To this end, *in vivo* studies have demonstrated that Ruxolitinib improves splenomegaly and survival in a murine JAK/STAT dependent MPN model after only 3 weeks of

treatment. Treatment with ruxolitinib also reduced inflammatory cytokines and pSTAT3 levels in these mice suggesting an *in vitro* and *in vivo* effect in JAK/STAT dependent malignancies¹⁵.

Safety

During the Phase I and Phase II development program, ruxolitinib was assessed in healthy volunteers, subjects with various degrees of renal or hepatic impairment, in subjects with rheumatoid arthritis, prostate cancer, multiple myeloma, myelofibrosis (MF), ploycythemia vera and essential thrombocythemia. The aggregate safety database for ruxoltinib included 679 subjects treated in 6 studies. Hematologic events were the most frequently reported adverse events (AE)s however, the majority of these were of Grades 1-2, seldom leading to study drug discontinuation (<1% of subjects). Increased rates of anemia did result in an increase in packed red blood cell (PRBC) transfusion requirements for some ruxolitinib-treated patients but platelet transfusions while on ruxolitinib were rare. No Grade 4 events as it relates to biochemistry laboratory abnormalities of alanine aminotransferase (ALT), aspartate aminotransferase (AST) or cholesterol were reported. The Phase III safety dataset in MF patients shows that it was appropriate to individually adjust doses for patients according to their tolerability and efficacy. However, 124 patients (41.2%) required no dose reduction, indicating the starting dose of 15mg or 20mg BID was appropriate for these individuals. Of the 177 patients who had dose reduction, 91 patients (51%) had only one. Interruptions of dosing were less frequent than dose reductions, with 215 patients (71.4%) requiring no dose interruption. Of the 86 patients who had dose interruptions, 59 patients (19.6%) had only one dose interruption. The Phase III safety dataset in MF subjects showed that the only notable imbalances (ruxolitinib versus placebo or best available therapy [BAT]) in AEs related to hemorrhagic events were in Grade 1-2 skin and soft tissue bruising which did not lead to dose reduction or discontinuation. Similarly, the only notable imbalances (ruxolitinib versus placebo or BAT) in AEs related to infections were urinary tract infections and herpes zoster infections. A thorough QT study was conducted in 50 healthy subjects. There was no indication of a QT/QTc prolonging effect of ruxolitinib in single doses up that exceeded those proposed in this study¹⁶.

Efficacy

In two large phase 3 clinical trials, ruxolitinib has demonstrated efficacy in subjects with high-risk myelofibrosis. The first trial randomly assigned subjects to receive 15mg twice daily of ruxolitinib (155 subjects) or placebo (154 subjects). The primary endpoint of the study was defined as the proportion of subjects with a reduction in spleen volume of 35% or more at 24 weeks by means of magnetic resonance imaging (MRI). The primary end point was reached in 41.9% of subjects in the ruxolitinib group as compared with 0.7% in the placebo group (P<0.001). A reduction in spleen volume was durable as 67.0% of the subjects with a response had the response for 48 weeks or more. There was an improvement of 50% or more in the total symptom score, a myleofibrosis specific quality-of-life scoring system, at 24 weeks in 45.9% of subjects who received ruxolitinib as compared with 5.3% of subjects who received placebo (P<0.001)¹⁷. The second trial randomly assigned subjects to the same dose of ruxolitinib or best available therapy (BAT) defined by the treating physician. The primary end point was the percentage of subjects with at least a 35% reduction in spleen volume at week 48 by MRI or computed tomography. A total of 28% of the subjects in the ruxolitinib group met the primary endpoint as compared with 0% in the group receiving the best available therapy (P<0.001). At 48 weeks, the mean palpable spleen length had decreased by 56% with ruxolitinib but had increased by 4% with the best available therapy. The median duration of response with ruxolitinib was not reached, with 80% of subjects still having a response at a median follow-up of 12 months¹⁸.

2.4 Rationale for Ruxolitinib in CMML

GM-CSF signaling is both dysregulated and important for CMML survival *in vitro* and *in vivo* (see section 2.2). Although GM-CSF signaling is hallmarked by cytokine pleotropy, it appears that STAT5 is preferentially activated in the CMML disease phenotype. Our laboratory has shown that targeting GM-CSF activation leads to decreased viability in primary CMML patient samples. In the late 1990s, efforts were made to target this pathway. Frankel and colleges developed a GM-CSF molecule fused to diphtheria toxin that was highly toxic to CMML myeloid progenitors in

16/20 patient samples tested¹⁹. This led to a phase I clinical trial in relapsed/refractory acute leukemias. Unfortunately, unacceptable hepatoxicity was seen, even at moderate doses of compound, that did not allow for dose escalation²⁰. This hepatotoxicity is now thought to be Kupffer cell mediated.

The JAK kinases are the sentinel kinases responsible for the key phosphorylation event in many cytokine receptors, including GM-CSF. Parganas and colleges developed a JAK2 deficient murine model that showed that JAK2 is required to elicit GM-CSF mediated signaling²¹. Considering this, our laboratory explored JAK1/2 pharmacologic inhibition with SD1029 in primary CMML cells. SD-1029 is a selective JAK1/JAK2 (µM IC50) inhibitor that is not available for clinical use and has a similar JAK inhibition profile to ruxolitinib. In 3 CMML patient samples tested, SD-1029 increased apoptosis and decreased viability by ANNEXIN-V and DAPI staining in a dose dependent fashion. None of these subjects tested harbored a JAK2V617F mutation. Lastly, Ravandi and colleges recently published the results of a phase 2 trial using ruxolitinib in refractory leukemias. In this cohort, 4 CMML subjects were enrolled to take BID ruxolitinib (dose not available). It is reported that 2/4 CMML subjects demonstrated some degree of clinical benefit²². Although the nature of the benefit was not expounded upon, it provides further proof-of-principle that JAK inhibition may indeed result in responses in this disease. Our preliminary data, in addition to the extensive data demonstrating the role of GM-CSF in CMML, provides compelling evidence to explore JAK1/2 inhibition with ruxolitinib as a therapeutic target in CMML.

3 STUDY ENDPOINTS

3.1 Primary

- 3.1.1 The maximum tolerated dose (MTD) of ruxolitinib for the treatment of CMML. The MTD is defined as the highest dose where less than 33% of subjects experience a drug related predefined dose limited toxicity (DLT).
- 3.1.2 Proportion of subject achieving clinical benefit defined as hematologic improvement, complete remission, partial remission, or stable disease by the IWG 2006 criteria (see appendix B)

- 3.2 Secondary
- **3.2.1** Acute myeloid leukemia (AML) transformation according to WHO criteria.
- **3.2.2** Overall survival (OS).
- **3.2.3** Duration of response.
- 3.2.4 The Myeloproliferative Neoplasms Symptom Assessment Form (MPN-SAF) at baseline and at best response.
- 3.2.5 >50% decrease in splenic length as measured by physical exam if applicable
- **3.2.6** The suppression of pSTAT5 intracellular signaling after ruxolitinib in CMML subjects (pretreatment, at 1-2hr post treatment, cycle 2, cycle 4, and progression.)
- **3.2.7** Determine number of colonies formed in the presence of GM-CSF and/or ruxolitinib (pretreatment and progression) as a future predictor of response.
- 3.2.8 Mutational status in our CMML subjects by sanger sequencing of JAK2, c-CBL, N-RAS, K-RAS,RUNX-1, TET2, SRSF2, EZH2, ASXL1, and DNMT3a (pretreatment and progression).
- 3.2.9 Mutational status of JAK2 tyrosine kinase at time of progression by deep sequencing of JAK2 to include M929I, Y931C, G935R, R938L, I960V, E985K. (pretreatment and at progression)

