	2. To determine overall best response rates as measured by the international working group												
	criteria (2006). (phase II)												
	Secondary Objectives:												
	1. To determine the time to AML transformation of subjects on Ruxolitinib.												
	2. To determine the median overall survival.												
	3. To determine the duration of response.												
	4. To determine the change in symptom score from baseline to best response.												
	5. To determine the change in spleen length at 16 weeks												
	6. To determine the change in downstream targets of JAK2 on ruxolitinib.												
	7. To determine if the in vitro activity of ruxolitinib correlates to response rates.												
	8. To determine if a correlation exist between the presence of the known recurrent												
	mutations (JAK2, c-CBL, N-RAS, K-RAS, RUNX-1, TET2, SRSF2, EZH2, ASXL1,												
	and DNMT3a) and response to ruxolitinib												
	9. To determine non-V617F JAK2 mutations at end of study or progression and their												
	clinical relevance in the context of ruxolitinib.												
	chinear relevance in the context of fuxontinio.												
Study	Primary												
Endpoints	1. The maximum tolerated dose (MTD) of ruxolitinib for the treatment of CMML.												
Ziiupoiiio	The MTD is defined as the highest dose where less than 33% of subjects												
	experience a drug related predefined dose limited toxicity (DLT).												
	2. Proportion of subject achieving a hematological response, partial response,												
	complete response, or stable disease by the IWG 2006 criteria (see appendix B)												
	Secondary												
	3. Acute myeloid leukemia (AML) transformation according to WHO criteria.												
	4. Overall survival (OS).												
	5. Duration of response.												
	6. The Myeloproliferative Neoplasms Symptom Assessment Form (MPN-SAF) at												
	baseline and at best response.												
	7. >50% decrease in splenic length as measured by physical exam if applicable												
	8. The suppression of pSTAT5 intracellular signaling after ruxolitinib in CMML												
	subjects (pretreatment, at 1-2hr post treatment, cycle 2, cycle 4, and												
	progression.)												
1	9. Determine number of colonies formed in the presence of GM-CSF and/or												
	ruxolitinib (pretreatment and progression) as a future predictor of response.												

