
If dose escalation is completed as planned a maximum of 53 (24 phase 1 and 29 in phase 2) are expected to enroll at a rate of 3 subjects every 1 month for stage I. The first phase of the stage II will recruit 10 subjects at the MTD. If 1 response are seen by 17 weeks on Ruxolitinib, then a total of 29 subjects will be accrued at the MTD to determine efficacy. Maximum accrual is 53 subjects.

Analysis of the following secondary endpoints will be of exploratory nature:

- 1. Acute myeloid leukemia (AML) transformation according to WHO criteria.
- 2. Overall survival (OS).
- 3. Duration of response.
- 4. The Myeloproliferative Neoplasms Symptom Assessment Form (MPN-SAF) at baseline and at best response.
- 5. >50% decrease in splenic length as measured by physical exam
- 6. The suppression of pSTAT5 intracellular signaling after ruxolitinib in CMML subjects (pretreatment, at 1-2hr post treatment, cycle 2, cycle 4, and progression.)
- 7. Determine number of colonies formed in the presence of GM-CSF and/or ruxolitinib (pretreatment and progression) as a future predictor of response.
- 8. Mutational status in our CMML subjects by sanger sequencing of JAK2V617F, c-CBL, N-RAS, K-RAS,RUNX-1, TET2, SRSF2, EZH2, ASXL1, and DNMT3a (pretreatment and progression).
- 9. Mutational status of JAK2 tyrosine kinase at time of progression by deep sequencing of JAK2 to include M929I, Y931C, G935R, R938L, I960V, E985K. (pretreatment and at progression)

Laboratory Correlates

Phases 1 and 2

The pharmacokinetics of ruxolitinib has been extensively studied in subjects with myeloid malignancies. Ruxolitinib is quickly absorbed with peak levels at 1 to 3 hours after ingestion of the tablet. Because of this, subjects will take their first dose of ruxolitinib in the clinic. At that time, and three hours after taking the tablet, peripheral blood will be collected and processed in the lab of [name] in the Stabile Research Building (SRB) at the Moffitt Cancer and Research Institute as described in section 16.

Using processed peripheral blood, pSTAT5 will be measured by flow cytometry at the time of tablet ingestion and 3 hours later. Bone marrow aspirates will also be used to perform colony formation assay as described in section 16 and to collect a minimum of 100 ug of DNA to interrogate the mutational status of the cohort studied as described in section 16.

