5 STUDY DESIGN

This is a phase 1/2, two-stage, sequential cohort dose escalation study. In phase 1, subjects will be allocated to BID doses of 10 mg/d up to 40mg/d. The starting dose will be 10 mg/d (5mg BID). Each cohort will include up to 6 subjects. Once MTD is reached, 10 additional subjects will be treated during the first stage of phase 2 (stage 1) at the MTD. The tiral will be terminated if 1 or fewer respond. If the trial goes on to the second stage, a total of 29 patients will be studied to determine efficacy in phase 2.

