15.2 Sample Size/Accrual Rate

If dose escalation is completed as planned, no more than 53 subjects are expected to enroll onto this study at a rate of approximately 3 subjects every month. For the Phase 2 study the Simon's optimal two-stage design will be employed to test the null hypothesis that response rate (RR) equals to 10% versus the alternative that RR equals to 30%. If the treatment is actually not effective, there is a 0.05 probability of concluding that it is. If the drug is actually effective, there is a 0.19 probability of concluding that it is not. The probability of early terminating the trial at the end of first stage under the null is 0.74. After testing the treatment dose on 10 patients in the first stage, the trial will be terminated if 1 or fewer desired respond. If the trial goes on to the second stage, a total of 29 patients will be studied. If the total number responding is less than or equal to 5, the drug is rejected. A sample size of 29 from Phase 2 produces a two-sided 95% CI with a width equal to 0.38 (±19) when the sample proportion is 0.50 that is the maximum width for a CI with an given sample sizes.

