15.5 Efficacy Analysis: ITT

This analysis will include all subjects who have received any protocol treatment, regardless of patient eligibility or duration of treatment. Those who have no response assessment data due to reasons such as drop out of the study, withdrawal consent, or lost to follow-up will be treated as non-responders for various response evaluations. The proportion of subjects achieving a complete platelet response will be summarized. A 95% exact binomial confidence interval of the proportion will also be provided for all participants treated at the MTD. In addition, a second analysis of evaluable subjects will be performed. Evaluable subjects are defined as those who complete at least 8 weeks of therapy an complete there first treatment bone marrow biopsy and aspirate to evaluate study drug response.

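### Stable disease is in the declared phase 2 primary endpoint, but the Simon test uses an undefined response rate and the efficacy analysis names a third quantity

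*Combined protocol and SAP*

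**What the plan says.** - **Endpoint.** Section 3.1.2 declares "Proportion of subject achieving clinical benefit defined as hematologic improvement, complete remission, partial remission, or stable disease by the IWG 2006 criteria". The synopsis list of primary endpoints also runs to "complete response, or stable disease by the IWG 2006 criteria (see appendix B", without the clinical-benefit label.
- **Hypothesis.** Section 15.2 is to "test the null hypothesis that response rate (RR) equals to 10% versus the alternative that RR equals to 30" per cent. It does not define that rate or refer to 3.1.2.
- **Decision rule.** In Section 15.2, after 10 subjects, "the trial will be terminated if 1 or fewer desired respond"; after 29, "If the total number responding is less than or equal to 5, the drug is rejected". Section 5 gives the same first-stage rule: the trial "will be terminated if 1 or fewer respond".
- **Accrual text.** The synopsis paragraph on sample size reads differently: "If 1 response are seen by 17 weeks on Ruxolitinib, then a total of 29 subjects will be accrued at the MTD".
- **Analysis.** Section 15.5: "The proportion of subjects achieving a complete platelet response will be summarized". It adds an exact 95% interval. No other proportion is named there.
- **Definitions.** Section 14 and Appendix B define stable disease as falling short of a partial response without progression for more than 8 weeks. Section 14 restricts pathologic response to CR, marrow CR and PR.

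**The concern.** The endpoint, the hypothesis test and the efficacy analysis describe three different quantities, and no passage links them. Whether the trial stops at 10 subjects, and whether the drug is rejected at 29, depends on who is counted.

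Take a hypothetical first stage with one hematologic improvement and three subjects with stable disease. Excluding stable disease the count is 1 and the trial stops; including it the count is 4 and the trial continues. In a single-arm trial, leaving this open means the responder definition could be settled after the outcomes are known.

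**Working it through.** **Inputs (Section 15.2).** First stage n1 = 10, stop at r1 = 1 or fewer; total n = 29, reject the drug at r = 5 or fewer; null 10%, alternative 30%. Stated: type I error 0.05, type II error 0.19, early stopping under the null 0.74.

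**Formulas.** With b(x; n, p) the binomial probability:

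- Early stopping = Σ b(x; 10, p) for x = 0 to r1.
- P(declare effective) = Σ b(x; 10, p) × P(Bin(19, p) ≥ 6 − x) for x = r1 + 1 to 10.
- Expected N = 10 + 19 × (1 − early stopping).

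**Step 1: reproduce the plan.** At p = 0.10:

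- Early stopping = 0.3487 + 0.3874 = 0.7361.
- Type I error = 0.1937 × 0.1150 (x = 2) + 0.0574 × 0.2946 (x = 3) + 0.0112 × 0.5797 (x = 4) + 0.0015 × 0.8649 (x = 5) + 0.0001 (x ≥ 6) = 0.0223 + 0.0169 + 0.0065 + 0.0013 + 0.0001 = 0.0471.
- Expected N = 10 + 19 × 0.2639 = 15.0.

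At p = 0.30, P(declare effective) = 0.8051, so type II error is 0.1949. A search with type I error at most 0.05 and power at least 0.80 returns 1/10, 5/29 as Simon's optimal design. The plan's figures are correct for whatever event has a 10% null rate.

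**Step 2: reading A, stable disease does not count.** Step 1 applies unchanged. The declared primary endpoint then has no hypothesis, no decision rule and no named analysis.

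**Step 3: reading B, stable disease counts.** The relevant p is the rate of HI, CR, PR or stable disease on an inactive drug. The documents do not give it, so the values below are assumptions.

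| Assumed inactive-drug rate | P(declare effective) | Early stopping |
|---|---|---|
| 10% | 0.047 | 0.74 |
| 15% | 0.20 | 0.54 |
| 20% | 0.43 | 0.38 |
| 30% | 0.81 | 0.15 |
| 40% | 0.95 | 0.05 |
| 50% | 0.99 | 0.01 |

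The false-positive rate passes 0.05 at p = 0.1015.

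**Step 4: what Section 15.5 would analyse.** Section 14 defines platelet response for baseline counts below 50 × 10⁹/L, and 4.2.1.1 excludes counts below 35 × 10⁹/L. On that definition only subjects entering between 35 and 50 × 10⁹/L could achieve the one proportion 15.5 names. Appendix B instead sets the platelet-improvement threshold at 100 × 10⁹/L.

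**Step 5: the synopsis accrual text, read literally.** Continuing on 1 response means r1 = 0. At p = 0.10:

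- Early stopping = 0.9¹⁰ = 0.3487.
- Type I error gains the x = 1 term: 0.0471 + 0.3874 × 0.0352 = 0.0471 + 0.0136 = 0.0607.
- Expected N = 10 + 19 × 0.6513 = 22.4.

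The two rules disagree when exactly 1 of 10 responds: probability 0.387 at p = 0.10 and 0.121 at p = 0.30. Only stopping at 1 or fewer reproduces the stated 0.05, 0.19 and 0.74.

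**The case against.** The strongest reply is that response plainly excludes stable disease. Objective 1.1.2 asks for overall response rates, the synopsis objective and Section 15.1 speak of overall best response, and stable disease is defined as failing to reach a partial response. On this view the Simon test addresses the stated primary objective, and the stray item is stable disease in the endpoint line. The large probabilities in Step 3 belong only to the other reading and rest on rates the documents do not supply.

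Much of this stands. The two readings are not evenly balanced, and Step 3 is a sensitivity range, not evidence that the error rate is inflated. But none of these passages defines the rate tested in 15.2. The stable-disease wording cannot supply the definition, because it also fits a subject with hematologic improvement but no partial response, whom 3.1.2 counts separately. The treatment rules also mix the terms: Section 7 continues treatment for responders, while 9.3 stops it for lack of clinical benefit, which 3.1.2 defines to include stable disease. If the objection is accepted in full, the declared primary endpoint is still untested and 15.5 still names a different proportion.

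Three smaller points are fair:

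- The synopsis accrual sentence may have lost a greater-than sign, so Step 5 should carry little weight beyond prompting a correction.
- The primary endpoint refers to Appendix B, which largely settles the platelet threshold for that endpoint.
- The 10–15% response rate in Section 2.1 concerns only the myeloproliferative variant, so it does not show that 10% is the wrong null for all CMML.

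**Conclusion.** The concern holds and must be fixed. Followed as written, the plan declares one endpoint, tests an undefined one and reports a third. The Simon calculation itself is right.

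The consequence depends on the reading. With stable disease excluded, the better-supported reading, the stated error rates stand but the declared primary endpoint has no test. With it included, the stated type I error and early-stopping probability hold only if the combined rate on an inactive drug is about 10%; at assumed rates of 15% to 50% the rule would pass an inactive drug with probability 0.20 to 0.99. Those rates are assumptions. The inconsistency does not depend on them.

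**What to change.** Name one event in the synopsis, 3.1.2, 15.2 and 15.5, and use it at both Simon stages.

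**Low-cost choice: CR, PR or HI by Appendix B, excluding stable disease.**

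- State that HI without PR counts as a response, and whether marrow CR counts (3.1.2 omits it).
- Keep 10% versus 30% and the 1/10, 5/29 rule, and give the source of the 10% null. If the true null were 15%, the upper end of the range in Section 2.1, the rule would pass 20% of the time.
- In 15.5, replace complete platelet response with this endpoint and its exact 95% interval.
- Report clinical benefit including stable disease as a descriptive secondary proportion.

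**If stable disease stays in the primary endpoint,** state and justify the null and alternative for the combined rate and recalculate. For an assumed 20-point difference, type I error 0.05 and power 0.80:

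| Null vs alternative | Optimal n | Minimax n |
|---|---|---|
| 15% vs 35% | 34 | 28 |
| 20% vs 40% | 43 | 33 |
| 30% vs 50% | 46 | 39 |
| 40% vs 60% | 46 | 39 |
| 50% vs 70% | 43 | 37 |

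**In the same amendment:** bring the synopsis accrual sentence into line with Sections 5 and 15.2; reconcile the platelet thresholds in Section 14 and Appendix B; and align the start of duration of response, which Section 14 ties to platelet response only.

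**Cost.** The low-cost choice needs a protocol amendment to the primary endpoint and matching text edits, with no extra subjects or procedures. The headline proportion will be lower than one that includes stable disease. The documents do not give enrolment status at Version 15, so the amendment should record what response data had been seen when the definition was fixed.
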